#### **9.2.4 Exploratory Efficacy Analyses**

Additional efficacy analysis includes the following endpoints at all visits in Period 1:

- Change from baseline in individual components of ACR response;
- ACR20/50/70 response rates;
- Change from baseline in DAS28 (CRP) and DAS28 (erythrocyte sedimentation rate [ESR]);
- Change from baseline in CDAI and SDAI;
- Change from baseline in morning stiffness (severity and duration);
- Proportion of subjects achieving LDA and proportion of subjects achieving CR based on DAS28 (CRP), DAS28 (ESR), Simplified Disease Activity Index (SDAI), and CDAI criteria;
- Proportion of subjects achieving MCID in change from baseline in HAQ-DI (defined as change from baseline in HAQ-DI  $\leq -0.3$ ) among those with baseline HAQ-DI  $\geq 0.3$ ;
- ACR/EULAR Boolean remission;
- Change from baseline in EQ-5D-5L;
- Change from baseline in SF-36;
- Change from baseline in FACIT-F;
- Change from baseline in RA-WIS.

For binary endpoints, point estimate and 95% CI using normal approximation will be provided for the response rate for each randomized treatment group. Point estimate, 95% CI and p-value will be provided for the treatment comparison between each upadacitinib

---

dose group and the combined placebo group using the Cochran-Mantel-Haenszel test adjusting for stratification factor prior bDMARD use. Only nominal p-value will be provided, and the 95% CI will be based on normal approximation. NRI will be used as primary analysis and OC will be used as sensitivity analysis.

For continuous endpoints, the LS mean and 95% CI will be reported for each randomized treatment group. The LS mean treatment difference and associated 95% CI and p-values between each upadacitinib dose group and the combined placebo group will be provided using MMRM model with fixed effects of treatment, visit and treatment-by-visit interaction, prior bDMARD use and baseline value as covariate. Only nominal p-value will be provided.

### **9.2.5 Handling of Multiplicity**

[figure not shown]
The overall type I error rate of the primary and ranked key secondary endpoints for the two doses will be strongly controlled using a graphical multiple testing procedure. Specifically, the testing will utilize the endpoint sequence of primary endpoint followed by the ranked key secondary endpoints in the order as specified in Section 9.2.3, and will begin with testing the primary endpoint using  $\alpha$  of 0.025 for each dose. Continued testing will follow a pre-specified  $\alpha$  transfer path which includes downstream transfer along the endpoint sequence within each dose as well as cross-dose transfer. Adjusted p-values for the primary and ranked key secondary endpoints will be provided based on the testing procedure.

The graphs for the testing procedures are provided in Figure 3 and Figure 4, for US/FDA and EU/EMA regulatory purposes respectively. In the graph, the arrows specify the  $\alpha$  transfer paths. Once an endpoint is rejected (i.e., deemed significant) at its assigned significance level, its significance level will be transferred to subsequent endpoint(s) following the arrow(s). If more than one arrow originates from an endpoint, the significance level for this endpoint (once rejected) will be split between multiple subsequent endpoints following the arrows. The numbers on the arrows denote the weights for transferring and (possibly) splitting significance levels. Specifically, the

[figure not shown]
weight 1 denotes 100% transfer of significance level, and the weight  $\frac{1}{2}$  denotes 50 – 50% splitting of significance level.

In addition, the last two endpoints in the graph, which are change from baseline in FACIT-F for high dose and low dose, will be tested in sequence at  $\alpha = 0.05$  after all previous endpoints in both doses are deemed significant.

**Figure 3. Graphical Multiple Testing Procedure for US/FDA Regulatory Purposes**

**Figure 4. Graphical Multiple Testing Procedure for EU/EMA Regulatory Purposes**

## 9.2.6 Efficacy Subgroup Analysis

The primary efficacy endpoint will be examined in the subgroups listed in [Table 3](#) below. Treatment difference between each upadacitinib dose and the combined placebo group will be presented with point estimate and 95% confidence interval using normal approximation. No p-value will be provided for subgroup analysis. If any of the resulting subgroups has fewer than 10% of the planned study size (i.e., < 60 subjects), the subgroup analyses for that variable will not be presented.

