5.2.1 Inclusion Criteria

1. Adult male or female, at least 18 years old.
2. Diagnosis of RA for ≥ 3 months who also fulfill the 2010 ACR/EULAR classification criteria for RA.
3. Subjects have been receiving csDMARD therapy ≥ 3 months and on a stable dose for ≥ 4 weeks prior to the first dose of study drug.
 - Subjects must have failed at least one of the following: MTX, sulfasalazine, or leflunomide.
 - Subjects with inadequate response to hydroxychloroquine and/or chloroquine can only be included if they have also failed MTX, sulfasalazine, or leflunomide.
 - The following csDMARDs are allowed (stable dose for ≥ 4 weeks prior to the first dose of study drug): oral or parenteral MTX (15 to 25 mg/week; or

≥ 10 mg/week in subjects who are intolerant of MTX at doses ≥ 15 mg/week), sulfasalazine (≤ 3000 mg/day), hydroxychloroquine (≤ 400 mg/day), chloroquine (≤ 250 mg/day), and leflunomide (≤ 20 mg/day).

- A combination of up to two background csDMARDs is allowed EXCEPT the combination of MTX and leflunomide.
4. Subject meets both of the following disease activity criteria:
 - a. ≥ 6 swollen joints (based on 66 joint counts) and ≥ 6 tender joints (based on 68 joint counts) at Screening and Baseline Visits; and
 - b. hsCRP ≥ 3 mg/L (central lab) at Screening Visit.
 5. Stable dose of NSAIDs, acetaminophen, oral corticosteroids (equivalent to prednisone ≤ 10 mg), or inhaled corticosteroids for stable medical conditions are allowed but must have been at a stable dose ≥ 4 weeks prior to the first dose of study drug.
 6. Subjects with prior exposure to at most one bDMARD may be enrolled (up to 20% of study population). Specifically, prior to enrollment:
 - a. Subjects with limited exposure to bDMARD (< 3 months) OR
 - b. Subjects who are responding to a bDMARD therapy but had to discontinue due to intolerability (regardless of treatment duration).
 7. Subjects must have discontinued bDMARD therapy prior to the first dose of study drug. The washout period for bDMARDs prior to the first dose of study is specified below or at least five times the mean terminal elimination half-life of a drug:
 - ≥ 4 weeks for etanercept;
 - ≥ 8 weeks for adalimumab, infliximab, certolizumab, golimumab, abatacept, and tocilizumab;
 - ≥ 1 year for rituximab OR ≥ 6 months if B cells have returned to pre-treatment level or normal reference range (central lab) if pre-treatment levels are not available.

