8.1.4.1.1 Primary Efficacy Variables

The primary endpoint in Period 1 (at Week 12) for US/FDA regulatory purposes is listed in Section 5.3.3.1.1. The primary endpoint in Period 1 (at Week 12) for EU/EMA regulatory purposes is also listed in Section 5.3.3.1.1. Analyses will be conducted separately for US/FDA regulatory purposes and EU/EMA regulatory purposes; for each set of analyses, only one primary endpoint is specified.

Analysis of the primary endpoint will be conducted on the FAS based on treatment as randomized. Comparison of the primary endpoint will be made between each upadacitinib group and the combined placebo groups using the Cochran-Mantel-Haenszel test adjusting for main stratification factors. For the primary analysis, Non-Responder Imputation (NRI) will be used. The analysis will be repeated using Observed Cases (OC). Supportive analysis will also be conducted on the Per Protocol Analysis Set.

The primary efficacy analyses will also be performed in demographic subgroups including age, gender, weight, body mass index, race, and geographical region to assess the consistency of the treatment effect. Additional subgroup analyses based on baseline disease characteristics and stratification factors will also be conducted.

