#### **4.2 Overall Study Design and Plan**

This is a Phase 3 multicenter study that includes two periods. Period 1 is a 12-week, randomized, double-blind, parallel-group, placebo-controlled period designed to compare

---

the safety and efficacy of upadacitinib 30 mg QD and 15 mg QD versus placebo for the treatment of signs and symptoms of subjects with moderately to severely active RA who are on a stable dose of csDMARDs and have an inadequate response to csDMARDs. Period 2 is a blinded long-term extension period to evaluate the long-term safety, tolerability, and efficacy of upadacitinib 30 mg QD and 15 mg QD in subjects with RA who have completed Period 1. Starting with Amendment 6, all subjects will receive open-label upadacitinib 15 mg QD, including those currently on upadacitinib 30 mg QD.

The study is designed to enroll approximately 600 subjects at approximately 230 study centers worldwide to meet scientific and regulatory objectives without enrolling an undue number of subjects in alignment with ethical considerations. Therefore, if the target number of subjects has been enrolled, there is a possibility that additional subjects in screening will not be enrolled.

The study duration includes a 35-day screening period; a 12-week randomized, double-blind, parallel-group, placebo controlled treatment period (Period 1); a 248-week blinded long-term extension period (Period 2); and a 30-day follow-up period (call or visit).

Subjects who meet eligibility criteria will be randomized in a 2:2:1:1 ratio to one of four treatment groups:

- Group 1: Upadacitinib 30 mg QD, N = 200 (Period 1) → Upadacitinib 30 mg QD (Period 2)
- Group 2: Upadacitinib 15 mg QD, N = 200 (Period 1) → Upadacitinib 15 mg QD (Period 2)
- Group 3: Placebo, N = 100 (Period 1) → Upadacitinib 30 mg QD (Period 2)
- Group 4: Placebo, N = 100 (Period 1) → Upadacitinib 15 mg QD (Period 2)

Randomization is stratified by prior exposure to bDMARD (yes/no) and geographic region.

Subjects must have been on a stable dose of csDMARD(s) for  $\geq 4$  weeks prior to the first dose of study drug and must remain on a stable dose until Week 24; the csDMARD dose may be decreased only for safety reasons.

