## **4.3 Sample Size**

The planned total sample size of 600 for this study provides at least 90% power for a 21% difference in ACR20 response rate at Week 12 (assuming a placebo ACR20 response rate

of 37%), as well as at least 90% power for a 22% difference in LDA response rate at Week 12 (based on DAS28 [CRP] [assuming a placebo LDA response rate of 15%]), at two sided significance level of 0.025 and accounting for a 10% dropout rate. This sample size will also provide at least 90% power for most of the key secondary endpoints, including change from baseline in DAS28 (CRP), change from baseline in HAQ-DI, ACR50 response rate, CR based on DAS28 (CRP), and SF-36 PCS, at two-sided significance level of 0.025 and accounting for a 10% dropout rate.

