**Table 3. Subgroups for Efficacy Analysis**

Subgroup Factor	Categories
Age	< 40, [40, 65), ≥ 65
Sex	Male or Female
Weight	< 60 kg or ≥ 60 kg
BMI	< 25 or ≥ 25
Race	White, Black or African American, American Indian or Alaska Native, Native Hawaiian or Other Pacific Islander, Asian, Other
Geographic Region	North America, South/Central America, Western Europe, Eastern Europe, Asia, Other
Duration of RA diagnosis	< 5 year or ≥ 5 year
Baseline Rheumatoid Factor Status	Positive or Negative
Baseline Anti-CCP Antibody Status	Positive or Negative
Baseline both RF positive and Anti-CCP positive	Yes or No
Baseline DAS28(hsCRP)	≤ 5.1 or > 5.1
Prior bDMARD use	Yes or No

## 9.2.7 Summary of Efficacy Analysis for Period 1

[Table 4](#) below provides the overview of the efficacy analyses for Period 1 to be performed on different endpoints.

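### The SAP's 60-subject subgroup rule lets one sparse category remove a whole factor: race is very likely affected if any level is 5% or less, and region depends on the mix

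*SAP*

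**What the plan says.** Protocol 8.1.4.1.1 states: "The primary efficacy analyses will also be performed in demographic subgroups including age, gender, weight, body mass index, race, and geographical region". The purpose given is to assess consistency of the treatment effect, and no minimum size is attached. The same paragraph adds subgroup analyses by stratification factor. Region is one of the two stratification factors, so it is covered twice.

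SAP 9.2.6 makes presentation conditional. The trigger is "If any of the resulting subgroups has fewer than 10% of the planned study size (i.e., < 60 subjects"); the consequence is that "the subgroup analyses for that variable will not be presented". The trigger is one category, and the consequence falls on the variable.

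Table 3 gives race six categories: "White, Black or African American, American Indian or Alaska Native, Native Hawaiian or Other Pacific Islander, Asian, Other". It also gives region six: "North America, South/Central America, Western Europe, Eastern Europe, Asia, Other". Neither document says that sparse levels are pooled, or that only the small level is withheld. Section 9.2.6 provides estimates and 95% confidence intervals for the subgroups, without p-values.

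**The concern.** A size floor protects readers from very imprecise estimates. That is a reason to withhold the small category. It is not a reason to withhold large categories of the same factor, whose precision does not depend on the small one. With six levels, the table appears only if the rarest level reaches 60, so the least informative level decides whether the others are seen.

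What is at stake is the consistency assessment that the protocol describes. Region has some extra weight. Randomization is stratified by it, but the Cochran-Mantel-Haenszel test in SAP 9.2.1 adjusts only for prior bDMARD use. I find no other planned Period 1 efficacy analysis that looks at the effect by region.

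**Working it through.** **Inputs.** Planned size 600 (SAP 4.3). Allocation 2:2:1:1, which is 200:200:200 once the placebo groups are combined (SAP 4.2). Threshold and consequence from SAP 9.2.6. Six levels each for race and region (SAP Table 3). No expected or actual counts by race or region are given, so every share below is an assumption.

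**The plan's own figure.** 0.10 × 600 = 60. This reproduces the stated threshold.

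**Is display possible at all?** Six levels at the threshold need 6 × 60 = 360 of 600 subjects, so it is. The largest level can then hold at most (600 − 5 × 60)/600 = 50%.

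**Chance that one category reaches 60.** With X ~ Binomial(600, p), P(X ≥ 60) is:

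| Assumed share p | Expected count | P(X ≥ 60) |
|---|---|---|
| 1% | 6 | 1e-39 |
| 3% | 18 | 1e-15 |
| 5% | 30 | 4e-7 |
| 7% | 42 | 0.4% |
| 8% | 48 | 4.5% |
| 9% | 54 | 21% |
| 10% | 60 | 52% |
| 12% | 72 | 94% |
| 15% | 90 | 99.99% |

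**Race.** The factor is shown only if all six levels reach 60, so the chance of display cannot exceed that of the rarest level. If any one level has a true share of 5% or less, the chance of display is at most about 4e-7.

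**Region.** Chance that all six regions reach 60, from 200,000 multinomial draws of 600 subjects for each assumed mix:

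| Assumed mix | Region shown |
|---|---|
| Six equal regions | > 99.9% |
| 20, 20, 20, 20, 12, 8% | about 4% |
| 25, 20, 20, 20, 10, 5% | about 0% |
| 50, 10, 10, 10, 10, 10% | about 1.6% |

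In the last mix every level has an expected count of at least 60, yet the table is almost always lost.

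**What the floor protects against.** At exactly 60 subjects there are about 20 per arm. Using the SAP 4.3 planning rates for ACR20 (37% on placebo, 37 + 21 = 58% on active), the 95% half-width for the difference is 1.96 × √(0.37 × 0.63/20 + 0.58 × 0.42/20) = 0.30. For LDA (15% and 15 + 22 = 37%) it is 1.96 × √(0.15 × 0.85/20 + 0.37 × 0.63/20) = 0.26. These intervals are wide, so a floor at category level is reasonable.

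**The case against.** - **The SAP limits presentation, not performance, and the protocol leaves analysis detail to the SAP.** This is fair. A reader might infer that the SAP cancels analyses the protocol promises, but the text supports only that they are not presented. The point still stands in practice, because a consistency analysis that is not presented informs nobody.
- **Race and region can be shown under the rule.** A reader might infer that these tables can never appear, or that region is probably lost. Neither follows: 360 of 600 subjects would satisfy the rule, and the mix is unknown.
- **The phrase about resulting subgroups may exclude empty levels, or refer to levels after collapsing.** It is ambiguous. Excluding empty levels would help only if the sparse level had no subjects, since 1 to 59 still triggers the rule. No collapsing is specified.
- **Subgroup results are descriptive and outside the multiplicity procedure, and the study objectives do not mention race or region.** This is correct, and it limits the consequence. Consistency is the protocol's stated purpose for the subgroup analyses; it is not a primary objective.
- **For a two-level factor, dropping the factor is sensible.** Agreed. Prior bDMARD use has a cap and no floor ("Subjects with prior exposure to at most one bDMARD may be enrolled (up to 20% of study population"), so at most 0.20 × 600 = 120 subjects and possibly fewer than 60. There is then nothing to pool with, and showing only the other level would not assess consistency.
- **Period 1 is closed.** SAP 11.1 says Period 1 was reported under v2.0 and that v3.0 governs only future long-term reporting. Editing 9.2.6 now changes no existing output. Section 9.2.6 is not named among the v3.0 changes, so the rule was probably carried over, but v2.0 is not supplied. The documents do not show that any table was actually withheld.

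**Conclusion.** The concern holds for factors with more than two levels. Followed as written, the rule hides well-populated categories because of an unrelated sparse one, and the imprecision safeguard does not need this.

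For race, suppression is very likely if any one of the six levels has a true share of 5% or less. That share is an assumption, not a figure from the documents. For region, the outcome runs from almost always shown to almost never shown across plausible mixes, so no prediction is justified. All probabilities assume 600 subjects are enrolled, as planned.

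The primary estimates, the tests and the alpha allocation are unaffected. What may be lost is descriptive evidence on consistency of effect.

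**What to change.** For factors with more than two levels, replace the last sentence of SAP 9.2.6 with wording to this effect:

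*Categories with fewer than 60 subjects will be pooled with other small categories of that factor (race: White, Asian, all other; region: small regions combined with Other). A pooled category still below 60 is not presented, and the remaining categories are presented.*

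Two-level factors may keep the present rule.

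Because Period 1 has been reported, the practical step is to check which race and region tables were withheld and issue those as supplementary descriptive tables from the locked data. They should be labelled post hoc where the pooling is chosen now.

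The cost is one SAP sentence and, at most, a rerun of the affected descriptive tables. The downside is that pooled categories are heterogeneous and should be read as such.

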**Table 3. Subgroups for Efficacy Analysis**

Subgroup Factor	Categories
Age	< 40, [40, 65), ≥ 65
Sex	Male or Female
Weight	< 60 kg or ≥ 60 kg
BMI	< 25 or ≥ 25
Race	White, Black or African American, American Indian or Alaska Native, Native Hawaiian or Other Pacific Islander, Asian, Other
Geographic Region	North America, South/Central America, Western Europe, Eastern Europe, Asia, Other
Duration of RA diagnosis	< 5 year or ≥ 5 year
Baseline Rheumatoid Factor Status	Positive or Negative
Baseline Anti-CCP Antibody Status	Positive or Negative
Baseline both RF positive and Anti-CCP positive	Yes or No
Baseline DAS28(hsCRP)	≤ 5.1 or > 5.1
Prior bDMARD use	Yes or No

## 9.2.7 Summary of Efficacy Analysis for Period 1

[Table 4](#) below provides the overview of the efficacy analyses for Period 1 to be performed on different endpoints.

**Table 4. Summary of Efficacy Variables and Corresponding Analyses for Efficacy Analysis in Period 1**

Efficacy Variables	Analysis Method
Primary Variables	

 
ACR20 response at Week 12a
 
LDA as measured by DAS28 (CRP) at Week 12b
 
	
 
Point estimate and 95% CI of the response rate for each upadacitinib dose group and the combined placebo group. The 95% CI will be based on normal approximation.
 
Point estimate, 95% CI and p-value for the treatment comparison between each upadacitinib dose group and the combined placebo group, where the p-value is constructed using the Cochran-Mantel-Haenszel test adjusting for stratification factor prior bDMARD use. Both nominal p-value and adjusted p-value through the graphical multiplicity procedure described in Section 9.2.5 will be provided. The 95% CI will be based on normal approximation.
 
Subgroup analysis.
 
Imputation: NRI for primary analysis and OC for sensitivity analysis
 
Analysis Set: FAS and Per Protocol Analysis Set as supportive analysis (NRI only).
 

Key Secondary Variables	

Binary Endpoints:
 
 
ACR50/70 response at Week 12
 
ACR20 response at Week 12b
 
ACR20 response at Week 1
 
Proportion of subjects achieving LDA based on DAS28 (CRP) <math>\leq 3.2^a</math>
 
Proportion of subjects achieving Clinical remission (CR) based on DAS28 (CRP)
 
Proportion of subjects achieving LDA based on CDAI <math>\leq 10</math>
 
	
 
Point estimate and 95% CI of the response rate for each treatment group. The 95% CI will be based on normal approximation.
 
Point estimate, 95% CI and p-value for the treatment comparison between each upadacitinib dose group and the combined placebo group using the Cochran-Mantel-Haenszel test adjusting for stratification factor prior bDMARD use. For ranked key secondary endpoints, both nominal p-value and adjusted p-value through the graphical multiplicity procedure described in Section 9.2.5 will be provided. The 95% CI will be based on normal approximation.
 
Imputation: NRI for primary analysis and OC for sensitivity analysis
 
Analysis Set: FAS
 

**Table 4. Summary of Efficacy Variables and Corresponding Analyses for Efficacy Analysis in Period 1 (Continued)**

Efficacy Variables	Analysis Method
Key Secondary Variables (continued)	

Continuous Endpoints:
 
 
Change from baseline in DAS28(CRP) at Week 12
 
Change from baseline in HAQ-DI at Week 12
 
	
 
LS mean, and 95% CI within each treatment group and LS mean, 95% CI and p-values between each upadacitinib dose group and the combined placebo group using ANCOVA model with treatment, prior bDMARD use and baseline value as covariates. Both nominal p-value and adjusted p-value through the graphical multiplicity procedure described in Section 9.2.5 will be provided.
 
Imputation: MI
 
Analysis Set: FAS
 

 
Change from baseline in SF-36 Physical Component Score (PCS) at Week 12
 
Change from baseline in morning stiffness (duration)
 
Change from baseline in FACIT-F
 
	
 
LS mean and 95% CI within each treatment group and LS mean, 95% CI and p-values between each upadacitinib dose group and the combined placebo group using MMRM model with fixed effects of treatment, visit and treatment-by-visit interaction, prior bDMARD use and baseline value as covariate. Both nominal p-value and adjusted p-value through the graphical multiplicity procedure described in Section 9.2.5 will be provided.
 
Analysis Set: FAS
 

Additional Variables (Summarized at all Visits up to Week 12)	

Binary Endpoints:
 
 
ACR20/50/70 response rate
 
Proportion of subjects achieving LDA and CR based on DAS28(CRP), DAS28 (ESR), SDAI, and CDAI criteria
 
Proportion of subjects achieving MCID in change from baseline in HAQ-DI among those with baseline HAQ-DI <math>\geq 0.3</math>
 
Boolean remission
 
	
 
Point estimate and 95% CI of the response rate for each treatment group. The 95% CI will be based on normal approximation.
 
Point estimate, 95% CI and p-value for the treatment comparison between each upadacitinib dose group and the combined placebo group using the Cochran-Mantel-Haenszel test adjusting for stratification factor prior bDMARD use. Only nominal p-value will be provided, and the 95% CI will be based on normal approximation.
 
Imputation: NRI for primary analysis and OC for sensitivity analysis
 
Analysis Set: FAS
 

